3.5. Withdrawal Criteria

The study will be discontinued after completion or upon recommendation from Data Safety and Monitoring board DSMB and with help from IRB.

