6. METHODS AND ASSESSMENTS

Based on the assumptions of successful extubation by day 5 of 50% of patients in the methadone group and 20% of patients in the control group and using a two tailed alpha level of 5%, a power of 80% our sample size calculation comparing proportions of two groups yielded 76. A 5% fallout as correction factor was 4 leaving us with a sample size of 80 patients. Statistical methods will include descriptive statistics and time to event analysis. Baseline characteristics will be reported. Data will be collected on a data collection sheet prior to transfer to REDCAPs database (Appendix 6). We will generate Kaplan-Meier curves and for comparison of hazard between groups we will use Cox regression (Cox proportional hazards model). Patients who die will be censored at time of death. Time of weaning will take into consideration only patients who were permanently disconnected from the ventilator. QTc values will be obtained from patient monitors and documented on data collection tool daily.

Randomization tables will be generated using REDCAPs database by study statistician. At the end of the study recorded information from REDCAPs will be exported to STATA for statistical analysis.

#UTHealth Houston

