8.2. Collecting, Recording and Reporting of Adverse Events

The principal investigator will be responsible for accurate documentation, investigation and followup as well as timely reporting of the following:

- 1- Any adverse event at the study site which in the opinion of the principal investigatoris both unexpected and related and places subjects or others at risk ofharm
- 2 Information that indicates a change to the risks or potential benefits of theresearch
- 3- An interim analysis or safety monitoring report indicates that frequency or magnitude of harms or benefits may be different than initially presented to the IRB
- 4 A paper is published from another study that shows that the risks or potential benefits of the research may be different than initially presented to the IRB
- 5 A breach of confidentiality
- 6 Change in FDA labelling or withdrawal from marketing of a drug, device or biologic used in a research protocol
- 7- Change to the protocol taken without prior IRB review to eliminate an apparent immediate hazard to a research participant
- 8 Incarceration of a participant in a protocol not approved to enroll prisoners
- 9- Event that requires prompt reporting to the sponsor
- 10- Sponsor imposed suspension
- 11- Complaint by a participant when the complaint indicates unexpected risks or cannot be resolved by the research team
- 12- Protocol deviation meaning an accidental or unintentional change to IRB approved protocol) that harmed participants or others or that indicates that participants or others may be at increased risk of harm
- 13- Unanticipated adverse device effect

Nursing staff and physicians will be notified to look out for the above. Any identified adverse event will be reported to the study PI who will discuss and inform the study coordinator aboutit.

The Principal investigator shall make a judgement about the expectedness of a problem. If the problem is an adverse event, the investigator shall make a judgement about the causality of the adverse event with respect to study intervention. The Principal investigator shall also evaluate whether protocol consent forms are needed.

The Principal investigator shall state whether the problem is expected or unexpected.

For adverse events the Principal Investigator shall evaluate the event and assess causality. He shall reveal evidence or arguments to suggest causal relationship

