10. SAMPLE SIZE AND STATISTICAL METHODS

10.1. Determination of Sample Size

Based on the assumptions of successful extubation by day 5 of 50% of patients in the methadone group and 20% of patients in the Non Methadone group and using a two tailed alpha level of 5%, a power of 80% our sample size calculation comparing proportions of two groups yielded 76. A 5% fall out as correction factor was 4 leaving us with a sample size of 80 patients.

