10.2. Statistical and Analytical Plans

Methadone when used at appropriate doses is considered safe and is an FDA approved medication. We will not be performing safety analysis. We will perform interim analysis after randomizing up to 50%(40) patients. Categorial variable will be compared using the student Chisquared test and continuous variables will be compared using the T-test. Interim analysis will be performed by an independent statistician blinded for the treatment allocation. The statistician will report to the data safety and monitoring committee. The DSMB will discuss the results of the interim analysis with the statistician and a steering committee and in a joint meeting will decide on continuation of the trial.

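### The interim look at 40 of 80 patients has no stated purpose, endpoint, boundary or final level, so nothing in the plan protects its two-sided 5%

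*Combined protocol and SAP*

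**What the plan says.** Section 10.2 (Statistical and Analytical Plans) commits to one look: "We will perform interim analysis after randomizing up to 50%(40) patients". On who does it: "Interim analysis will be performed by an independent statistician blinded for the treatment allocation". On what follows: "The DSMB will discuss the results of the interim analysis with the statistician and a steering committee and in a joint meeting will decide" on whether the trial goes on. The same section names the chi-squared test and the t-test, but ties neither to the interim nor to an outcome. It also states "We will not be performing safety analysis".

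The only significance level is in the sample size text of sections 6 and 10.1: "using a two tailed alpha level of 5%, a power of 80" per cent, for 50% against 20% extubated by day 5, giving 76 patients and then 80.

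Other sections mention stopping or an interim analysis, but give no statistical rule:

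- Section 3.5: "The study will be discontinued after completion or upon recommendation from Data Safety and Monitoring board DSMB and with help from IRB".
- The Safety Monitoring Plan has the DSMB meet quarterly and rule on whether the study continues.
- Section 8.2 lists, among reportable events, the case where "An interim analysis or safety monitoring report indicates that frequency or magnitude of harms or benefits may be different" from what the IRB was first told.

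**The concern.** A look whose result can end the trial is a second chance to reject the null hypothesis, unless a rule prevents that. Section 10.2 does not say whether the trial may stop for efficacy, futility or harm, in which direction, on which outcome, or at what level at either look. The reported p-value would then have no defined error rate, and a rule chosen after the data are seen cannot repair that credibly.

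Two consequences would follow if an ordinary p<0.05 were used at the interim. The chance of a false claim of benefit would rise. A trial stopped at 20 per arm would also tend to report an effect well above the true one.

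A smaller matter is who sees the results. Section 7.5 blinds the outcome assessors but not the treating physicians and nurses. The results are discussed with a steering committee whose membership is not given. The text therefore does not exclude that comparative interim results reach people who treat or enrol patients.

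**Working it through.** **Inputs.** Two-sided 5%, 80% power, 50% v 20%, 76 then 80 patients (section 10.1); 1:1 allocation (section 4.1); one look at 40 of 80 (section 10.2), so about half the information. An interim critical value of 1.96 is an assumption; the documents give none.

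**The plan's own figure.** By the arcsine formula, h = 2·asin(√0.5) − 2·asin(√0.2) = 0.6435. Then n = 2(1.960 + 0.842)²/h² = 37.9, so 38 per arm and 76 in total; 76/0.95 = 80. The pooled-variance formula gives 39 per arm (78). The stated size is reproduced, and it is a single-look size.

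**Error with 5% at both looks (normal theory).** Under the null, Z1 (interim) and Z2 (final) have correlation √0.5 = 0.707.

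- P(Z1 > 1.96) = 0.0250.
- P(Z1 ≤ 1.96 and Z2 > 1.96) = 0.0166.
- False claim that methadone is better: 0.0250 + 0.0166 = 0.0416, against 0.0250 for one look. This holds whether or not the trial may also stop in the other direction.
- Total two-sided error, stopping for benefit only: 0.0416 + 0.0250 (false finding of methadone worse at the final test) = 0.0666.
- Total two-sided error, stopping in either direction: 2 × 0.04156 = 0.0831.

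If the information fraction runs from 0.40 to 0.55, the two totals run from 6.8% to 6.6% and from 8.6% to 8.1%.

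**Exact check for day-5 extubation.** Binomial enumeration, chi-squared test without continuity correction, common rate 20% to 50%:

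| Rule | 20 then 40 per arm | 19 then 38 per arm |
|---|---|---|
| One look | 4.8% to 5.7% | 4.9% to 5.2% |
| 5% twice, stop for benefit only | 6.6% to 7.0% | 6.7% to 7.0% |
| 5% twice, stop in either direction | 8.3% to 8.5% | 8.3% to 8.9% |
| p<0.001 for benefit, then 5% | 4.8% to 5.7% | 4.9% to 5.2% |

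The right-hand column is the case of 76 evaluable patients. Section 3.6 replaces drop-outs, so it is a sensitivity check rather than the expected case.

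**Looks that do not inflate.** At 20 then 40 per arm, a stop only for harm (methadone worse at p<0.05, no efficacy claim) gives 4.0% to 4.9%. A stop only for futility (methadone behind) gives 2.5% to 2.9%. A pooled look makes no comparison between arms, so it gives no extra chance to reject.

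**Exaggeration.** At a true 50% v 20% and p<0.05 at the interim, 53% of trials stop early. Their mean estimated difference is 41 points, against a true 30.

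**A p<0.001 efficacy boundary (|Z| > 3.29), final test at 0.05.** Total error is 5.01% in normal theory. In the exact calculation at 20 then 40 per arm it is at most 0.01 percentage points above one look. Power at 50% v 20% is 81.7%, the same as for one look (80.0% for both with 76 evaluable). At a true 30 points, 8% of trials stop early, with a mean estimate of 55 points. With 4 of 20 controls extubated, stopping needs 15 of 20 on methadone (p = 0.0005; 14 of 20 gives 0.0015), against 10 of 20 for p<0.05.

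**The case against.** The strongest reply is that nothing in the documents says 5% will be used at the interim, or that the arms will be compared at all. The statistician is to be blinded to allocation, which fits a pooled review as well as a comparison of coded arms. The sentence naming the tests is not tied to the interim. This stands, and it makes every percentage above conditional. It does not remove the gap, because the plan does not say which case applies. Blinding alone would not protect the level either: comparing coded arms is still a look at the difference.

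A DSMB may use judgement. That is true, but judgement without a written rule leaves the error rate of the final test undefined.

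Four stronger readings are tempting, and the documents do not support them:

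- *The trial's error rate is 8.3%.* That needs an interim level and a stopping direction that are not stated.
- *Stopping for benefit only halves the problem.* The two-sided total is lower (6.7% v 8.3%), but the false claim of benefit is 4.16% under both rules.
- *The documents contradict each other on who decides.* In section 10.2 the DSMB is the body that decides, in a joint meeting. That is compatible with section 3.5 and the Safety Monitoring Plan.
- *Section 8.2 shows the purpose of the look.* It is a general list of reportable events, which also covers device effects, and it plans no analysis.

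The trigger, randomization of the 40th patient, matters little for day-5 extubation. Section 2.5 counts day 5 from intubation and entry follows more than 72 hours of ventilation, so the gap is at most about two days. It would matter more for ventilator-free days.

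**Conclusion.** The point holds as an omission: section 10.2 plans a look that bears on continuation, no section supplies a purpose, endpoint, boundary or final level, and the stated 5% is a single-look level. It is worth fixing before the look takes place.

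If the arms are compared at half the information and 0.05 is used at both looks with stopping for benefit, a false claim of benefit rises from 2.5% to about 4.2%, roughly two thirds above nominal (0.0416/0.0250 = 1.66). If the look is pooled, or can stop the trial only for futility or harm, there is no inflation, though a futility stop can cost power. A reader might infer that treating staff will see comparative results; the text only fails to exclude it.

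Which outcome and test are primary is a separate matter. Section 2.2 names ventilator-free days, section 2.5 names extubation by day 5, and section 6 says "for comparison of hazard between groups we will use Cox regression". The interim should follow whatever is confirmed there. The normal-theory error rates apply to any of these; the exact rates, power and early-stopping figures are for day-5 extubation with a chi-squared test.

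**What to change.** Add to section 10.2, once the primary outcome and its test are settled:

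> The interim analysis compares the confirmed primary outcome, by its primary test, after the first 40 randomized patients have all reached that outcome's time point. The trial may stop for efficacy only if methadone is better with two-sided p<0.001. The final test uses two-sided 0.05. The blinded statistician reports results by coded arm; only the DSMB holds the code. The look may / may not also stop the trial for futility or harm [choose].

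The decoding step is needed because the rule is directional and a statistician blinded to allocation cannot say which arm is ahead. If no efficacy stop is intended, or the look is pooled, say that instead; 0.05 then stands unchanged.

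Replace the joint-meeting sentence with:

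> The DSMB reviews comparative results in closed session and passes only a recommendation to the steering committee.

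This is a precaution, and it fits the recommendation wording already in section 3.5.

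Other boundaries also hold 5%: O'Brien-Fleming (p<0.0052, then p<0.0480) or Pocock (p<0.0294 at both looks). The p<0.001 rule is suggested because it leaves the final test at 0.05.

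**Cost.** A few sentences, no extra patients, and no power lost against a single look (81.7% with 80 patients). Early efficacy stops become rarer, 8% instead of 53% at a true 30 points, and those that occur are still exaggerated (mean 55 points). The steering committee no longer sees comparative interim data.

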4.1 Allocation

All patients admitted to the medical ICU will be screened for eligibility. Group assignment will be done using the randomization module of the Research Electronic Data Capture (REDCap) platform. Patients will be randomized in a 1 to 1 ratio, using permuted blocks of 4 or 6, into one of two groups: methadone group and the Non-Methadone group. The randomization will be stratified based on location where patients will be recruited.

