6.1. Randomization and Blinding

Patients will be randomized between two groups, the Methadone group (MG) and the Non-Methadone group (NG). Randomization tables will be generated using REDCap database. Randomization will be stratified by Center of data collection. The investigators evaluating the primary and secondary outcomes will be blinded to the group assignments. The study participants, pharmacists, physicians and nurses taking care of the patients will not be blinded.

Assignment of patients to study groups will be by random allocation by randomization tables. There will be two randomization tables, one for Memorial Hermann Cypress and the other for Memorial Hermann Texas Medical Center. Patients predetermined to receive methadone will receive oral methadone which comes in 5mg tablets. Tablets will be crushed and administered via the feeding tube if patients are still on enteral feeding at the time the medication is administered. Patients predetermined not to receive methadone will continue treatment following usual care per hospital weaning protocols.

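### Randomisation is stratified by hospital but no named analysis includes hospital, which costs some efficiency if the two ICUs differ materially

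*Combined protocol and SAP*

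**What the plan says.** Section 4.1 states "The randomization will be stratified based on location where patients will be recruited" and "Patients will be randomized in a 1 to 1 ratio, using permuted blocks of 4 or 6". Section 6.1 repeats the stratification ("Randomization will be stratified by Center of data collection") and fixes the number of strata: "There will be two randomization tables, one for Memorial Hermann Cypress and the other for Memorial Hermann Texas Medical Center".

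The comparisons are named in two places. Section 10.2 has one sentence on tests: "Categorial variable will be compared using the student Chisquared test and continuous variables will be compared using the T-test". Section 6 adds time-to-event methods: "We will generate Kaplan-Meier curves and for comparison of hazard between groups we will use Cox regression (Cox proportional hazards model"). Neither section mentions hospital as a stratum, factor or covariate, and nothing elsewhere says the analysis will reflect the stratified randomisation. The sample size in section 10.1 compares two proportions and assumes "successful extubation by day 5 of 50% of patients in the methadone group and 20% of patients in the Non Methadone group".

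**The concern.** Blocking within hospital makes the two arms nearly equal in size at each site. A difference in extubation rate between the ICUs therefore largely cancels out of the arm comparison. A chi-squared or t-test that ignores hospital still counts that difference as random variation, so its standard error is too large and its true type I error falls below the nominal 5%. For Cox regression the mechanism differs: leaving out a prognostic factor tends to pull the estimated hazard ratio toward 1.

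The stake is efficiency. The trial has 80 patients and is sized for 80% power at a 30-point effect, so there is little slack. Leaving hospital unmentioned also leaves open a choice between adjusted and unadjusted results after the data are seen.

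**Working it through.** **Inputs from the documents.** Two strata, 1:1 allocation, blocks of 4 or 6 (sections 4.1 and 6.1). Rates of 50% v 20%, two-sided alpha 5%, power 80%, 76 patients before dropout and 80 after (section 10.1).

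**Inputs assumed.** The gap between hospitals, the split of patients between them, and an effect that is the same at both. The documents give none of these, so a range is shown.

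**1. The plan's sample size.** Arcsine formula: h = 2·arcsin√0.5 − 2·arcsin√0.2 = 0.6435, and n = 2(1.960 + 0.842)²/h² = 37.9, so 38 per arm and 76 in total. Then 76/0.95 = 80. The plan's figure reproduces as an unstratified two-proportion design. (The pooled-variance formula gives 39 per arm, or 78.)

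**2. Standard error.** With patients split equally and a gap g between hospitals in each arm, the variance term seen by an unstratified comparison is 0.5×0.5 + 0.2×0.8 = 0.41. The within-hospital part is 0.41 − 2(g²/4) = 0.41 − g²/2. The ratio of stratified to unstratified standard error is:

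- g = 10 points: √(0.405/0.41) = 0.994
- g = 20 points: √(0.390/0.41) = 0.975
- g = 30 points: √(0.365/0.41) = 0.944

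**3. Power for extubation by day 5.** 19 patients per arm at each hospital, constant 30-point effect, Pearson chi-squared v Cochran-Mantel-Haenszel (CMH) without continuity correction. Power is summed exactly over the four binomial counts.

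| Site gap | Control rates | Methadone rates | Chi-squared | CMH by hospital |
|---|---|---|---|---|
| 0 | 20% / 20% | 50% / 50% | 80.0% | 79.3% |
| 10 points | 25% / 15% | 55% / 45% | 80.1% | 79.9% |
| 20 points | 30% / 10% | 60% / 40% | 80.5% | 81.6% |
| 30 points | 35% / 5% | 65% / 35% | 81.3% | 84.6% |

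Simulation at the same settings agrees to within 0.1 point (80.0 v 79.4, 80.1 v 79.9, 80.6 v 81.7, 81.3 v 84.6). At the full 80 patients, with blocks of 4 or 6 actually generated, the pattern is the same: 82.3% v 82.1%, 82.2% v 82.2%, 82.7% v 83.7% and 83.1% v 86.3%. With a 60/20 split between hospitals and a 20-point gap it is 82.5% v 83.3%.

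**4. Type I error of the plain chi-squared test.** Take a common rate of 35% in both arms. The variance term is 2×0.35×0.65 = 0.455 unstratified and 0.455 − g²/2 within hospital. The effective critical value is 1.96×√(0.455/(0.455 − g²/2)):

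- 10 points: 1.96×√(0.455/0.450) = 1.971, so 4.9%
- 20 points: 1.96×√(0.455/0.435) = 2.005, so 4.5%
- 40 points: 1.96×√(0.455/0.375) = 2.159, so 3.1%

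The exact binomial sums round to the same values, and simulation gave 4.8%, 4.4% and 3.1%.

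**5. t-test.** For an equal split and a gap of g standard deviations, the unadjusted standard error is too large by a factor √(1 + g²/4): 0.8% at 0.25 SD, 3.1% at 0.5 SD, 11.8% at 1 SD.

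**6. Time to event.** The log-rank test stands in for Cox, with 80 patients, an assumed treatment hazard ratio of 2, exponential times censored at 30 days, and 6,000 runs. Power unstratified v stratified is 83.0% v 83.5% at a site hazard ratio of 1.5, 79.4% v 83.2% at 2, and 70.3% v 82.1% at 3. With no treatment effect, the unstratified test's type I error is 4.9%, 4.5% and 3.0%. The pull of the hazard ratio toward 1 is a known property of the model and was not itself simulated.

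**The case against.** The best case for leaving the plan alone runs as follows.

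- **The gain is often nil.** A reader might infer that power is lost whenever the two sites differ. It is not, at any visible size: at a 10-point gap the stratified test gains nothing, and at 20 points it gains about 1 point. This stands.
- **Large gaps are assumption.** Both units are medical ICUs under one set of eligibility criteria (sections 3, 3.3 and 3.4), and one sedation weaning protocol is appended for usual care. Nothing in the documents shows a gap of 30 points or more. This stands. It does not exclude a smaller gap.
- **The target is met.** In every row of the power table the chi-squared test reaches the planned 80%. What is forgone is power above the target. This stands for the binary endpoint.
- **Cox is left open.** A reader might infer that the plan commits to an unadjusted Cox model, or that every planned test has error bars that are too wide. Section 6 names the model without listing covariates or strata, which is silence. The harm there is mainly a hazard ratio pulled toward 1.
- **The quoted sentence is ambiguous.** In section 10.2 it sits between two sentences on the interim analysis, and no section names the final test of the day-5 proportion. This stands, and it is a further reason to name that test.

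None of this removes the mismatch: hospital is a declared design factor and is absent from every analysis that is named.

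**Conclusion.** The mismatch is real and its effect is modest. If extubation rates differ materially between the hospitals, the plain chi-squared and t-tests are conservative, and a Cox model without hospital tends to understate the effect. For the day-5 proportion, stratifying gains nothing up to a 10-point gap, about 1 point of power at 20 and about 3 points at 30. The time-to-event comparison is more sensitive, with about 4 points at an assumed site hazard ratio of 2.

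All of these sizes rest on assumed site rates and on a treatment effect that is the same at both hospitals. A reader might infer that the significance tests are invalid or that false positives increase. The calculations show the opposite: the true type I error is at or below 5%. This is a minor to moderate efficiency point, not a validity failure.

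**What to change.** In sections 6 and 10.2:

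- Name a Cochran-Mantel-Haenszel test stratified by hospital as the test of extubation by day 5, with a stratified risk difference and 95% confidence interval.
- Stratify the Cox model by hospital.
- Include hospital as a factor in the length-of-stay comparisons, for example linear regression on arm and hospital in place of the t-test.
- Confirm that site is exported with the randomisation data. The two site-specific tables should supply it, but the Appendix 6 data sheet lists no site field.

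The cost is a change of wording, plus one variable to confirm. No extra patients are needed. If the hospitals turn out alike, the stratified test gives up at most about 1 point of power (80.0% v 79.3% at 38 per arm).
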